3.7 Preliminary Safety in Humans

The first 6 cohorts of this study have been completed including subjects receiving a single 5 mg dose. No significant adverse effects were reported in any subjects receiving a single or multiple doses of the LSALT peptide.

3.8 Study Rationale

Acute kidney injury is a devastating complication for patients undergoing surgery, diagnostic imaging or in the context of critical illness. Currently there are no effective therapies to prevent or minimize acute kidney injury. Inflammation is an important factor

¹ An allergic reaction is marked by the activation of the immune system by an allergen and includes signs that involve the skin, nose/throat, upper airway, GI tract, lungs and cardiovascular system. While the animals exhibited clinical features that would be seen in an allergic reaction, given its self-limited nature and severity, and the fact that they occurred only during the infusion, the findings are considered to represent a non-immune infusion reaction. Thus, the effects were considered pseudo-allergic or anaphylactoid.

in the pathogenesis of acute kidney injury. Given its favorable initial toxicology profile, the administration of LSALT peptide to target inflammation and prevent acute kidney injury has the potential to provide a significant clinical impact. Since LSALT peptide is a new drug, this phase I study to evaluate safety and pharmacokinetics is the first step needed to advance the LSALT peptide for the prevention of acute kidney injury in humans.

A third MAD cohort of 5 mg administered intravenously daily for 3 days is being proposed to obtain additional pharmacokinetic data.

4.0 OBJECTIVES

4.1 Primary Objective

To determine the safety and tolerability of 4 single and multiple ascending doses of LSALT peptide in healthy participants.

4.2 Secondary Objective

To evaluate the pharmacokinetics and pharmacodynamics of LSALT peptide in healthy participants

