1.0 SYNOPSIS

Inflammation resulting from infection or injury leads to tissue damage and eventually organ dysfunction/failure due to the effects of recruited immune cells. This process is regulated by many biological events which include the recruitment and adhesion of circulating leukocytes to endothelial cells prior to infiltration of the target tissue. Dipeptidase-1 is a common receptor that regulates the adhesion of circulating leukocytes to endothelial cells.

LSALT is a 16 amino acid peptide drug and a selective non-enzymatic dipeptidase-1 antagonist. LSALT peptide prevents leukocyte adhesion to endothelial cells creating numerous indications for targeting inflammation in the context of microbial and non-microbial (sterile) tissue injury. In pre-clinical mouse models, LSALT peptide has proven efficacious in preventing acute kidney injury induced by ischemia-reperfusion, toxins and sepsis. LSALT peptide has a favorable toxicology profile with little drug-related toxicity observed in animal studies. This is a first-in-human phase I clinical study to evaluate the safety and pharmacokinetics of single and multiple ascending doses of the LSALT peptide.

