3.5 Drug Metabolism and Pharmacokinetics

Plasma levels of LSALT peptide were measured post-intravenous dosing of 100, 250 and 450 mg/kg in rats. Terminal elimination half-lives of 0.66 – 1.17 hr and MRT_{obs} values of 0.58 – 0.85 hr were observed for LSALT peptide. The AUC_{0- ∞} was linear and close to proportional with dose.

LSALT peptide is stable in human plasma for up to 90 minutes with no detectable metabolic/proteolytic fragments as measured by mass spectrometry. LSALT peptide is undetectable in whole blood in the absence of phosphoric acid due to red or white blood cell binding. In human whole blood, 90% or more of the LSALT peptide is contained within the cellular compartment. LSALT peptide however is compatible with blood and does not induce red blood cell hemolysis. Work is ongoing to identify LSALT peptide volume of distribution, tissue biodistribution, and excretion.

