5.0 STUDY DESIGN

This is a double-blind, placebo-controlled, randomized, adaptive design single and multiple ascending dose study to evaluate the safety and pharmacokinetics of LSALT peptide in healthy participants.

To establish a safe starting dose of LSALT peptide, unblinded low dose escalation will first be performed in a small cohort of participants. 0.01 mg of LSALT peptide will be administered intravenously (IV) once. If no adverse effects are observed following 72 hours, subsequent single (n=1) participants will be administered escalating doses of 0.1 mg, 0.3 mg and 0.5mg every 72 hours. If no adverse effects are observed at the 0.5 mg dose, then the study will proceed to the first cohort of 8 participants (6 active treatment, 2 placebo per dose level) who will receive 1.0 mg of LSALT peptide in a double-blinded fashion. Safety, tolerability, pharmacokinetics (PK), and pharmacodynamics (PD) will be assessed before escalating to the next cohort. Dosing will be completed in two sequential cohorts of 8 participants using doses of 2.5 mg and 5.0 mg. The first 2 participants in each blinded cohort will act as sentinels (1 treatment, 1 placebo) who must show no adverse effects before continuing the study under the current design.

Once safety, PK and PD data are completed in the single ascending dose cohort, and the LSALT peptide is determined to be safe and well-tolerated by the Safety Review Committee (SRC), the multiple ascending dose arm of the study will proceed. The multiple ascending dose arm will consist of 2 cohorts of 8 participants receiving 2 independent doses of the LSALT peptide or placebo once or twice daily for 3 consecutive days. The doses for this arm of the study will consist of the 2 highest doses determined by the SRC to be safe in the SAD cohort. The first cohort will receive drug in a double-blinded fashion. Safety, tolerability, PK, and PD will be assessed before escalating to the next cohort. Each cohort will consist of 6 active treatment, 2 placebo per dose

level. The first 2 participants in each cohort will act as sentinels (1 treatment, 1 placebo) who must show no adverse effects before continuing the study under the current design.

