7.1 Single Ascending Dose (SAD) Cohort

7.1.1 Sample Size. The study sample size will be 4 + 24 participants for the SAD arm of the protocol. The first 4 participants will comprise a low dose escalation cohort, and 3 cohorts of 8 (6 treatment and 2 placebo) will comprise the single ascending dose cohorts.

7.1.2 LSALT Peptide Dosing. It is anticipated that seven single intravenous doses of LSALT peptide (0.01 mg, 0.1 mg, 0.3 mg, 0.5 mg, 1 mg, 2.5 mg and 5 mg) will be administered in this arm of the study.

The first 4 participants will each sequentially receive a single escalating low dose of the LSALT peptide (0.01 mg, 0.1 mg, 0.3 mg or 0.5 mg). Escalation to the next dose and participant will occur every 72 hours if no adverse effects are seen. Participants will then be enrolled in cohorts of 8 and randomized to treatment or placebo in a 3:1 ratio. The dose for the first SAD cohort will be 1 mg administered intravenously once over 2 hours. The first 2 subjects of each cohort will be sentinels (1 treatment, 1 placebo). Continuation of the study in each cohort will occur if no clinical or biochemical adverse effects are observed in the sentinels as determined by the Safety Review Committee (SRC). Escalation to the higher dose cohorts (2.5 mg and 5 mg) will occur after 10-14 days if no clinical or biochemical adverse effects are observed in the prior cohort.

A rationale for the proposed doses is based on the NOAEL in dogs (2.5 mg/kg) and the minimum effective dose in mice (0.1-1 μ g/kg). The human equivalent dose is 1.4 mg/kg. The 1 mg dose (16.7 μ g/kg in a 60 kg human) is 1200-fold less than the maximum tolerated dose of 20 mg/kg in dogs, 150-fold lower than the NOAEL and provides a safety factor of 83 relative to the calculated human equivalent dose. The 5 mg dose (83.3 mcg/kg in a 60 kg human) is 240-fold less than the maximum tolerated dose of 20 mg/kg in dogs, 30-fold less than the NOAEL and provides a safety factor of 17 relative to the calculated human equivalent dose. Based on the minimum therapeutic dose observed in mice (0.1 - 1 μ g/kg), a conservative first dose of 0.01 mg (166.7 ng/kg in a 60 kg human) is chosen to further increase the safety margin of the starting dose by 100-fold (i.e. 8400 x less than the human equivalent dose calculated from the NOAEL).

7.1.3 Confinement. Participants will be confined for 24 hours following infusion of the LSALT peptide or placebo.

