1. Vital signs dosing day (seated): pre dose (+/-30 mins), 1 hour (+/- 10mins), 2 hour (+/- 10 mins) 6 hours (+/- 15min) and 10 hours post completion of infusion (+/- 30 mins).
2. 12 lead electrocardiogram (supine): pre dose (+/- 30 mins), 2 hours (+/- 15 mins) and 8 hours post completion of infusion (+/- 30 mins)
3. Pregnancy test will be via serum B-hCG at Screening and a urine pregnancy test at pre dose (Study Day -1, Day 4, Day 8, Day 12) and follow up.

SAD Cohorts

- **Day -1.** Admission to unit; Participants will undergo a clinical evaluation including complete vital signs and physical examination, 12-lead electrocardiogram (supine), drugs of abuse and alcohol breath test, urinalyses and 25 ml of blood drawn for safety

laboratory investigations including CBC, clinical chemistries, coagulation profile (INR and PTT) and women of child-bearing age will have a urine pregnancy test to rule out pregnancy.

- **Day 1. Cohort 1.** Participants will undergo a clinical evaluation, including vital signs and 12-lead electrocardiogram .5 ml of blood will be drawn at 30 prior to LSALT peptide infusion for baseline PK measurements. LSALT peptide infusion will begin and run over 2 hours. 5 ml of blood will be drawn at 15 minutess, 30 minutes, 1, 2, 4, 6, 8, and 12 hours after the LSALT infusion has started.
- **Day 2.** Participants will undergo a clinical evaluation, including vital signs and symptom directed physical examination. 25 ml of blood will be drawn for laboratory investigations, including CBC, clinical chemistries, coagulation profile (INR and PTT) and 24 hour PK sample. An ECG will also be completed. If the participant shows no adverse events, they will be discharged from the unit.
- **Day 4.** Participants will undergo a clinical evaluation, including vital signs and a symptom directed physical examination. 25 ml of blood will be drawn for laboratory investigations, including 72 hour PK sample. An ECG will also be completed.
- **Day 7.** Participants will return for a clinical evaluation, including vital signs and a complete physical examination. 25 ml of blood will be drawn for laboratory investigations, including CBC, clinical chemistries and PK. A urinalysis, CXR and ECG will also be completed. Women of child-bearing age will have a urine pregnancy test to rule out pregnancy
- **Day 14. Cohort 2.** Conducted as per Cohort 1 to day 7.
- **Day 28. Cohort 3.** Conducted as per Cohort 1 to day 7.

Treatment and Assessment Timetable (SAD)

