7.2 Multiple Ascending Dose (MAD) Cohort

7.2.1 Sample Size. The study sample size will be 24 for the MAD arm of the protocol in cohorts of 8. Participants will be randomized to treatment or placebo in a 3:1 ratio. The first 2 subjects of each cohort will be sentinels (1 treatment, 1 placebo). Continuation of the study in each cohort will occur if no clinical or biochemical adverse effects are observed in the sentinels as determined by the Safety Review Committee (SRC). Escalation to the higher dose will occur if no clinical or biochemical adverse effects are observed after a 10 day follow-up period as determined by the SRC.

7.2.2 LSALT Peptide Dosing. The doses for the MAD cohorts will be determined by the SRC based on the results from the prior SAD and MAD arms of the study. These doses have been determined to be 1 mg, 2.5 mg and 5 mg. LSALT peptide will administered intravenously once daily for 3 days. The starting dose for the Phase 1 clinical study will be subject to change and reassessed based on the results from the SAD cohort and in accordance with FDAs guidance document for estimating a safe starting dose in initial clinical trials.

7.2.3 Confinement. Participants will be confined for days -1 to day 4 during the administration of the LASLT peptide.

7.2.4 Replacement. In the event of participant drop-out, participants from the reserve pool will be enrolled in the study and randomized.

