7.2.5 MAD Study Procedures

- **Day -29. Pretreatment Evaluation and Randomization.** 29 days prior to study initiation, enrolled participants will undergo informed consent, followed by a complete history and physical examination (including body weight and height) vital signs (seated), alcohol breath test, drugs of abuse test, baseline fasting laboratory studies (CBC, clinical chemistry) including coagulation profile (INR and PTT), urinalysis, 12-lead, electrocardiogram (supine) and chest x-ray (single PA view). Women of child-bearing age will have a β -hCG to rule out pregnancy. Participants will then be randomized.
- **Day -1.** Admission to unit. Participants will undergo a clinical evaluation including complete vital signs and physical examination, 12-lead electrocardiogram (supine), drugs of abuse and alcohol breath test, urinalyses, 25 ml of blood drawn for safety laboratory investigations including CBC, clinical chemistries, urinalysis and women of child-bearing age will have a urine pregnancy test to rule out pregnancy.
- **Day 1.** Participants will undergo clinical evaluation including vital signs. 5 ml of blood will be drawn at 30 minutes prior to LSALT peptide infusion for baseline PK measurements. LSALT peptide infusion will begin and run over 2 hours. 5 ml of blood will be drawn at 15, 30, 45 60, 75, 90, 105, 120, 125, 130, 135, 140 minutes, and 3 hours from the onset of the LSALT infusion.

- **Day 2.** Participants will undergo a clinical evaluation, including vital signs, a brief history and symptom directed physical exam. 25 ml of blood will be drawn for laboratory investigations, including CBC, clinical chemistries and coagulation profile (INR and PTT), urinalysis and 24 hour PK sample (from the onset of the first LSALT infusion). An ECG will also be completed. If the participant shows no adverse events, they will receive the second dose of the LSALT peptide.
- **Day 3.** Participants will undergo a clinical evaluation, including vital signs, a brief history and a symptom directed physical exam. If the participant shows no adverse events, they will receive the third dose of the LSALT peptide. 5 ml of blood will be drawn at 15, 30, 45 60, 75, 90, 105, 120, 125, 130, 135, 140 minutes, and 3 hours from the onset of the LSALT infusion.

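### Does the pharmacodynamic part of the secondary objective, which has no endpoint or analysis, call for a change to the SAP?

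*Protocol*

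**What the plan says.** Protocol 4.2 sets as the secondary objective "To evaluate the pharmacokinetics and pharmacodynamics of LSALT peptide in healthy participants". SAP 3.2 carries it over unchanged. Protocol 5.0 adds, for the single-dose part, that "Safety, tolerability, pharmacokinetics (PK), and pharmacodynamics (PD) will be assessed before escalating to the next cohort". It says the same for the multiple-dose part, and expects PD data to be complete before that part starts; SAP 3.3 restates this. SAP 3.5 names PD among the things the sample sizes are meant to inform, and says that no power calculation was made.

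The operative sections are narrower. Protocol 16 plans tabulations of demographics, safety and PK. SAP 4 lists four safety and two PK endpoints. SAP 5 defines the ITT, Safety, PK Concentration and PK Parameters populations. SAP 8 to 10 cover PK, the listing of antibody samples, and safety. SAP 12 records no change from the analysis planned in the protocol.

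The dosing sections give escalation criteria without naming PD. In Protocol 7.1.2, "Escalation to the higher dose cohorts (2.5 mg and 5 mg) will occur after 10-14 days if no clinical or biochemical adverse effects" are seen in the preceding cohort. In Protocol 7.2.1, "Escalation to the higher dose will occur if no clinical or biochemical adverse effects are observed after a 10 day follow-up period".

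**The concern.** An objective normally leads to a variable, a time point, a population and an analysis. Here PD leads to none of them. Candidate data do exist: Protocol 7.3.6 collects white cell counts and creatinine, and the Synopsis says that "LSALT peptide prevents leukocyte adhesion to endothelial cells". A report writer could therefore pick a white cell result after seeing the data and call it PD. Otherwise the objective could lapse with nothing said, since SAP 12 declares no changes.

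The disposition shells add to the impression that something was lost. The SAD shell has a row for a *Pharmacodynamic Parameters Population* and the MAD shell one for a *Pharmacodynamic Population*. SAP 5 defines neither.

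**Working it through.** **1. The plan's own figure.** The only sample-size figure is 52 participants (Protocol 6.3). It reproduces as 4 low-dose + 3 × 8 SAD + 3 × 8 MAD = 52. Each randomised part has 18 active and 6 placebo participants. The figure has no power basis, so nothing in it depends on a PD variable.

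**2. Where PD is named and where it is absent.**

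| PD named | PD absent |
|---|---|
| Protocol 4.2, SAP 3.2 (objective) | Protocol 7 (procedures, timetables, laboratory tests) |
| Protocol 5.0, SAP 3.3 (design text) | Protocol 15 and 16 (PK, statistics) |
| SAP 3.5 (sample-size rationale) | SAP 4 (0 of 6 endpoints), SAP 5 (0 of 4 populations) |
| Two disposition shell rows | SAP 8 to 10 and all titles in the list of tables, listings and figures |

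The gap is real, and it starts in the protocol.

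**3. SAP 12.** Its heading asks for changes from the analysis the protocol planned. Protocol 16 planned no PD analysis, so on this point the entry is literally correct.

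**4. Shell rows.** In the SAD shell the PD row comes straight after the PK Concentration Population, where the PK Parameters Population belongs. The enrolment listings print the PK Parameters Population in that position, so the row is probably a typing slip. In the MAD shell, *Pharmacokinetic Population* matches no SAP 5 heading, but the body of SAP 5.4 uses that name in its abbreviated form. The clear stray is the MAD PD row. No PD table or listing depends on either row.

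**5. Would an endpoint from collected data help?**

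*Timing.* The infusion lasts 2 h. On SAD Day 2, "25 ml of blood will be drawn for laboratory investigations, including CBC, clinical chemistries, coagulation profile (INR and PTT) and 24 hour PK sample". That sample is 24 h after the end of infusion by the SAD timetable, or 24 − 2 = 22 h after it by Protocol 7.3.6, which counts from onset. The MAD Day 2 draw is 24 − 2 = 22 h after the end of the first infusion. The MAD Day 4 draw is 72 h from first onset; with doses 24 h apart that is 72 − 48 − 2 = 22 h after the end of the third.

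Protocol 3.5 reports "Terminal elimination half-lives of 0.66 – 1.17 hr" in rats: 22/1.17 = 18.8 and 22/0.66 = 33.3 half-lives. The human half-life is not given. For assumed values of 1, 2, 4, 6 and 12 h, 22 h is 22, 11, 5.5, 3.7 and 1.8 half-lives.

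*Precision.* Take four groups of 6 within a part and a baseline covariate: 24 − 5 = 19 df, t = 2.093. In residual SD units the 95% half-widths are:

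- all active against placebo: 2.093 × √(1/18 + 1/6) = 0.99
- one dose against placebo: 2.093 × √(1/6 + 1/6) = 1.21

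**6. How large is the room for post hoc choice?** Contrasts = variables × post-dose visits × 3 doses. The timetables give blood counts on SAD Days 2 and 7 and on MAD Days 2, 4, 7, 14 and 21.

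- Two variables (white cells, creatinine): 2 × 2 × 3 + 2 × 5 × 3 = 12 + 30 = 42.
- Seven variables (adding an assumed five-part differential): 42 + 105 = 147.
- If tested at 5%: 42 × 0.05 = 2.1 and 147 × 0.05 = 7.4 expected chance positives.

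Protocol 7.3.6 also lists Day 4 laboratory draws. Adding SAD Day 4 gives 18 + 30 = 48 to 63 + 105 = 168 contrasts, and 2.4 to 8.4 chance positives. Scheduled draws rise from 48 + 120 = 168 to 72 + 120 = 192. These counts apply only if someone tests the laboratory data as PD. SAP 10.3 summarises them descriptively by treatment and plans no test.

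**The case for a change.** The strongest case for a change is that an objective with no variable can be neither met nor reported as unmet. An SAP update before unblinding would cost no visit, sample or participant. Naming one variable, one visit and one contrast per part would cut the 42 to 147 possible contrasts to 2. PD also appears in the design text as something assessed before escalation.

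Part of this stands. The objective and the analyses do not match, and a reader of the report is owed a sentence saying that PD was not evaluated. The design text in Protocol 5.0 and SAP 3.3 also differs from Protocol 7.1.2, 7.2.1 and 8.0, which rest escalation on adverse effects and laboratory abnormalities. Those passages must be reconciled by the sponsor; no view is offered here on which should govern.

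The rest does not carry. The multiplicity count presumes PD tests that no section, table or figure plans. A white cell endpoint chosen now would not be free of hindsight either: Protocol 3.7 says six cohorts are complete, the safety committee reviews data at each step (Protocol 8.0), and Grade 2 or higher events trigger unblinding (Protocol 9.9). It would be read about 22 to 24 h after infusion with roughly 1 SD of precision, so a null result would say little about an effect during infusion. The alternative, recording that PD is not evaluated, discloses the gap but alters no analysis.

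**Conclusion.** The mismatch is real but needs no change to the plan. Followed as written, the plan gives its safety and PK results in full and no PD result. No estimate, population or test is affected, and SAP 12 is not a misstatement. What remains is a missing definition that the study report can state plainly, and shell labels that a programmer would align with SAP 5 when building the tables.

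Adding an endpoint would be a debatable choice with little gain: half-widths of 0.99 SD (18 v 6) and 1.21 SD (6 v 6), at a time 19 to 33 rat half-lives after the infusion ends.

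This rests on three assumptions. The addendum, eCRF and schema were not seen, and any of them might designate a PD variable. The differential is listed only under baseline hematology, so its presence in later counts is assumed. The human half-life is unknown; towards 12 h, the top of the assumed range, the timing argument weakens (1.8 half-lives), but the precision argument does not.

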5.0 STUDY DESIGN

This is a double-blind, placebo-controlled, randomized, adaptive design single and multiple ascending dose study to evaluate the safety and pharmacokinetics of LSALT peptide in healthy participants.

To establish a safe starting dose of LSALT peptide, unblinded low dose escalation will first be performed in a small cohort of participants. 0.01 mg of LSALT peptide will be administered intravenously (IV) once. If no adverse effects are observed following 72 hours, subsequent single (n=1) participants will be administered escalating doses of 0.1 mg, 0.3 mg and 0.5mg every 72 hours. If no adverse effects are observed at the 0.5 mg dose, then the study will proceed to the first cohort of 8 participants (6 active treatment, 2 placebo per dose level) who will receive 1.0 mg of LSALT peptide in a double-blinded fashion. Safety, tolerability, pharmacokinetics (PK), and pharmacodynamics (PD) will be assessed before escalating to the next cohort. Dosing will be completed in two sequential cohorts of 8 participants using doses of 2.5 mg and 5.0 mg. The first 2 participants in each blinded cohort will act as sentinels (1 treatment, 1 placebo) who must show no adverse effects before continuing the study under the current design.

Once safety, PK and PD data are completed in the single ascending dose cohort, and the LSALT peptide is determined to be safe and well-tolerated by the Safety Review Committee (SRC), the multiple ascending dose arm of the study will proceed. The multiple ascending dose arm will consist of 2 cohorts of 8 participants receiving 2 independent doses of the LSALT peptide or placebo once or twice daily for 3 consecutive days. The doses for this arm of the study will consist of the 2 highest doses determined by the SRC to be safe in the SAD cohort. The first cohort will receive drug in a double-blinded fashion. Safety, tolerability, PK, and PD will be assessed before escalating to the next cohort. Each cohort will consist of 6 active treatment, 2 placebo per dose

level. The first 2 participants in each cohort will act as sentinels (1 treatment, 1 placebo) who must show no adverse effects before continuing the study under the current design.

